5.3 LIFESTYLE CONSIDERATIONS

During this study, participants are asked to:

- Refrain from using herbal medications (e.g. St. John's Wort), or medications that are sensitive to cytochrome CYP3A4 substrates or CYP3A4 modulators, such as fluconazole.

5.4 SCREEN FAILURES

Screen failures are defined as participants who consent to participate in the clinical trial but are not entered in the study. A minimal set of screen failure information is required to ensure transparent reporting of screen failure participants, to meet the Consolidated Standards of Reporting Trials (CONSORT) publishing requirements and to respond to queries from regulatory authorities. Minimal information includes demography, screen failure details, eligibility criteria, and any serious adverse event (SAE).

Individuals who do not meet the criteria for participation in this trial (screen failure) because Hydroxyurea dose or hemoglobin had not been stable for 3 months may be rescreened. Rescreened participants should be assigned the same participant number as for the initial screening.

5.5 STRATEGIES FOR RECRUITMENT AND RETENTION

- Target study sample size is 10 patients with any mix of male or female gender
- Anticipated accrual rate is 2-3 a month
- Participants will be recruited when they come to the PSV sickle cell clinic in Northern Virginia
- Potential participants will be identified by preview of patients scheduled for upcoming clinics. Potential participants will be pre-screened through electronic medical record. They will be approached during their clinic visit
- Recruitment flyer will be emailed and mailed to potential participants. It will also be handed to patients and families when they come to clinic.
- The study requires 5-6 months of participation, CRA will keep in constant contact with participants by telephone. \$150 plus the cost of a meal will be offered as compensation for completion of each CPET, to be paid to the participant, with parental consent if the participant is < age 18.
- Transportation to and from the exercise lab will be covered by the study
- A full CPET report that can be used for personal exercise and sports guidelines will be provided to each participant.
- This study population are patients with sickle cell anemia, who are all in minority groups historically under-represented. Our patient population includes African-Americans, Africans, Hispanics, and Middle Easterners.
- This is a pediatric study, therefore, the vulnerable population of minors are included by definition.

6 STUDY INTERVENTION

6.1 STUDY INTERVENTION(S) ADMINISTRATION

No text is to be entered in this section; rather it should be included under the relevant subheadings below.

6.1.1 STUDY INTERVENTION DESCRIPTION

The study intervention is voxelotor, taken orally. It will be used for the approved indication of sickle cell anemia. This is a single-arm study. There is no control intervention.

6.1.2 DOSING AND ADMINISTRATION

Participants will be instructed to take voxelotor 1500mg consisting of three 500mg-tablets once daily for at least 8 weeks. It can be taken with Hydroxyurea. If a participant misses a dose, the participant should resume normal dosing next day (i.e., the dose on the day after a day of a missed dose should not be increased or decreased). Voxelotor will be dispensed from the sickle cell clinic in bottles with 90 tablets each for a 30-day supply.

6.2 PREPARATION/HANDLING/STORAGE/ACCOUNTABILITY

No text is to be entered in this section; rather it should be included under the relevant subheadings below.

6.2.1 ACQUISITION AND ACCOUNTABILITY

Voxelotor tablets will be supplied in high-density polyethylene bottles with induction-sealed polypropylene child-resistant caps. Packaged and labeled drug product (voxelotor) will be supplied by GBT and shipped to the clinical site. Study drug will be dispensed at Visit 3 in bottles of 90 tablets. The PSV pharmacist will receive the bottles, which will be stored in a temperature controlled locked med room. The PI will dispense the drug. The study coordinator or PI will pick up/sign pharmacy log and dispense study drug to participant with instructions during the study visit.

The participants will bring the medicine bottle back to clinic each month. Unused pills will be counted and recorded. Dates of receipt, dispense, return, lot numbers, and pill counts will all be recorded in a log.

6.2.2 FORMULATION, APPEARANCE, PACKAGING, AND LABELING

Voxelotor comes in 500mg tablets that are film-coated, light yellow to yellow, oval shaped, biconvex, debossed with "GBT 500" on one side. It is packaged in bottles of 90 tablets with child-resistant closure.

6.2.3 PRODUCT STORAGE AND STABILITY

Voxelotor will be stored at controlled room temperature between 15 °C and 25°C (59°F to 77°F) in a secure, temperature-controlled storage area of the investigational site's clinic medication room which is a secure, locked environment with restricted access. No special procedures for the safe handling of voxelotor are required.

6.2.4 PREPARATION

Voxelotor is a tablet ready to be swallowed. There is no drug preparation.

6.3 MEASURES TO MINIMIZE BIAS: RANDOMIZATION AND BLINDING

Not applicable. There is no randomization.

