1 PROTOCOL SUMMARY

1.1 SYNOPSIS

Title:

The Effect of Voxelotor on Exercise Capacity of Youths with Sickle Cell Anemia

Study Description:

This study is a pilot, open-label, single-arm study to evaluate the effect of voxelotor on exercise capacity, as measured by cardiopulmonary exercise testing (CPET) in patients 12 years of age and older with sickle cell anemia (SCA). Voxelotor was recently approved for the treatment of SCA in patients 12 years and older. We hypothesize that exercise capacity will be improved by voxelotor treatment in sickle cell patients whether they are on Hydroxyurea or not. This study will assess exercise capacity by cardiopulmonary exercise testing (CPET) before and after 8 weeks of voxelotor therapy.

Objectives:

Primary Objective: To evaluate the effect of voxelotor on peak oxygen consumption (VO₂) in adolescents with SCA as assessed by change in CPET from baseline.

Secondary Objective: To correlate peak VO₂ with biochemical markers, including hemoglobin, reticulocyte count, bilirubin, lactate dehydrogenase, haptoglobin, % Hgb F expressing cells, P50 oxygen dissociation, point of sickling (POS), and dense cells.

Exploratory Objective: To evaluate the effect of voxelotor on HRQOL as assessed by patient-reported outcome (PGIC) and clinician-reported outcome (CGIC) at end of treatment study visit

Endpoints:

Primary endpoint: Change in Peak VO₂ from baseline

Secondary endpoint: Hemoglobin and biochemical markers of sickling and hemolysis

[figure not shown]
Exploratory endpoint: Clinician and Patient Global Impression of Change assessment (CGIC and PGIC)

Study Population:

1.1.1.1.1 Patients seen in the Pediatric Sickle Cell Program in Northern Virginia (Fairfax, VA) who have a genetically severe forms of sickle cell disease (including Hgb SS, Hgb Sbeta⁰thalassemia, or Hgb SC^{Harlem}) and are age 12 or older.

| | |
|--|--|
| Phase: | This is a single-center, open-label, single-arm longitudinal interventional pilot study. |
| Description of Sites/Facilities Enrolling Participants: | The outpatient sickle cell clinic of Pediatric Specialists of Virginia located in the Schar Cancer Institute on Inova Hospital Campus in Fairfax, VA. This pilot study aims to enroll 10 patients. |
| Description of Study Intervention: | During the open-label treatment period, all participants will receive voxelotor at a fixed dose of 1500mg (administered as three 500mg tablets) orally once daily for 8 weeks |
| Study Duration: | 12 months |

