4 STUDY DESIGN

4.1 OVERALL DESIGN

Hypothesis: Voxelotor improves exercise capacity in SCA patients.

Study type: single-center, open-label, single-arm longitudinal interventional pilot study

Methods: Patients with genetically severe forms of sickle cell disease age 12 or older will be enrolled from the PSV sickle cell clinic in Northern Virginia. A baseline CPET will be performed. Voxelotor will be initiated, and a second CPET will be performed. The CPET after the study intervention (voxelotor) will be compared to the baseline CPET. Each patient will be his/her own control.

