8 STUDY ASSESSMENTS AND PROCEDURES

8.1 EFFICACY ASSESSMENTS

Efficacy of study drug will be assessed as follows:

- CPET (cardiopulmonary exercise test) is non-invasive and will be performed using a motorized treadmill (Trackmaster Model TMX428, Full Vision, Inc.). Participants will have their nose clipped and breathe through a mouthpiece with a nonbreathing valve. Breath by breath gas exchange data will be collected and analyzed using a VMax Encore 29C metabolic cart (CareFusion Corp, San Diego, CA). The participants will have EKG leads and pulse oximetry monitoring while running on a treadmill that increases in incline incrementally to induce peak physical effort according to a modified Bruce protocol based on patient age, size, and exercise ability. A peak exercise response will be defined as a respiratory exchange ratio of greater than 1.1 or to patient's volitional fatigue. The patient exercises for 8-12 minutes. Approximately 1.5 hour will be allotted for the entire CPET visit, which will include checking in, explanation of the procedure, preparation and setup for the test, the exercise test itself, and post-test debriefing. This exercise test will be done twice by each participant: once before and once after starting the study drug. The CPET report will be provided to the participant.
- During exercise the following will be measured and recorded:
 - · 12-Lead ECG
 - · Pulse oximetry
 - · Blood Pressure
 - · Peak HR
 - · Peak VO₂ (ml/kg/min)

- · Peak VO₂ (L/min)
 - · Respiratory Exchange Ratio (RER)
 - · O₂ Pulse
 - · VE/VO₂
 - · VE/VCO₂
 - · VO₂/HR
 - · VAT (ventilatory anaerobic threshold)
 - · Percent VO₂ at VAT
- Blood will be drawn for study labs once before the study drug and once after. Study labs will be performed by the research laboratory of [name] at UCSF. Blood samples will be sent by FEDEX overnight.
 - Blood work as part of regular standard of care will continue to be done during the study.
 - The “Patient Global Impression of Change” and the “Clinician Global Impression of Change” single-question surveys will be completed by the participant and the clinician, respectively, at the final study visit.

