9.4.2 ANALYSIS OF THE PRIMARY EFFICACY ENDPOINT(S)

The primary endpoint is peak VO₂, which is a quantitative measurement from the CPET instrument. There will be a single measurement as a baseline and another single measurement after the study drug for each participant. Paired t-test will be used to compare the 2 peak VO₂s.

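### Section 6.3 sets aside measures against bias solely because there is no randomization, although the primary test depends on effort, the second test is always on drug, and no rule keeps effort or read-out alike at the two tests

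*Protocol*

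**What the plan says.** Section 6.3 is headed as covering randomization and blinding. Its entire content is "Not applicable. There is no randomization"; blinding is not discussed.

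Other sections describe the setting:

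- **Design.** Section 1.1: "This study is a pilot, open-label, single-arm study". Section 4.1: "Hypothesis: Voxelotor improves exercise capacity in SCA patients".
- **Order of tests.** Section 8.1: each participant is tested "once before and once after starting the study drug".
- **Nature of the test.** Section 8.1: participants are "running on a treadmill that increases in incline incrementally to induce peak physical effort". The same section fits the test to the individual, in these words: "according to a modified Bruce protocol based on patient age, size, and exercise ability".
- **End of the test.** Section 8.1 defines peak response as a "respiratory exchange ratio of greater than 1.1 or to" the patient's volitional fatigue.
- **Data for the primary analysis.** Section 9.4.2: "There will be a single measurement as a baseline and another single measurement after the study drug for each participant". The two values are compared by paired t-test.
- **Release of results.** Sections 5.5 and 8.1 promise each participant the CPET report and do not say when it is given.
- **Purpose.** Section 9.2 says the ten patients are to define the magnitude of change. Section 9.4.1 adds that the study is to justify a larger efficacy trial and that results are first analysed descriptively.

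**The concern.** Randomization protects against differences between groups. It has nothing to do with whether two tests on the same person are conducted and read in the same way, so its absence is no reason to call measures against bias inapplicable.

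The matter counts here because the endpoint depends on effort. A test that may stop at volitional fatigue has no required objective effort level. The treadmill protocol is fitted to exercise ability and is not stated to be the same at both tests. Test order and treatment coincide completely, and there is one value per side, so any mean difference in effort enters the paired difference in full. The paired t-test cannot separate it from a drug effect.

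At stake is the pilot's main product, the estimate of change that a larger trial would be built on.

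**Working it through.** **1. Is there a figure in the plan to reproduce?** No. The protocol gives no SD of change, significance level, sidedness or target effect, and section 9.2 says power cannot be calculated. The only benchmark is in section 2.2: a difference of about 10% in peak VO₂ before and after transfusion.

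**2. What in the protocol limits a difference in effort between the tests?**

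| Provision | What it controls | Does it equalise effort or mask the read-out? |
|---|---|---|
| Own-control comparison (4.2) | Variability between subjects | No |
| Stable hydroxyurea dose (5.1, 6.5); no recent transfusion (5.2) | Other causes of change | No |
| No peak VO₂ expectations communicated to patients (2.3.1) | Participant anxiety | In part, for participants only |
| Named treadmill and metabolic cart (8.1); exercise-lab quality control (10.1.8) | Instrument error | No rule on effort is stated |
| RER, peak HR and ventilatory threshold recorded (8.1); individual listings (9.4.8) | Allow effort to be compared afterwards | They could, but no rule uses them |

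Nothing in the document standardises encouragement, keeps the treadmill protocol the same, withholds the baseline value or sets an effort comparison.

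**3. Effect on the estimate.** If the drug is inert and the mean effort-related gain at the second test is b (in % of baseline), the expected estimate is 0 + b = b. Against the benchmark of about 10%, a gain of 1%, 2% or 3% is 10%, 20% or 30% of it.

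**4. Effect on the test, for illustration only.** Inputs: n = 10 (9.2) and the paired t-test (9.4.2) are from the protocol. The two-sided 5% level, the SD of change of 6–10% and the gain of 1–3% are assumptions.

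Standard error = SD/√10, that is 1.90, 2.53 and 3.16 percentage points for SD 6, 8 and 10.

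Noncentrality = b·√10/SD, with 9 degrees of freedom and critical value 2.262. Rejection rate = P(|T| > 2.262) under the noncentral t distribution.

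| Gain b | SD 6 | SD 8 | SD 10 |
|---|---|---|---|
| 0% (nominal) | 5% | 5% | 5% |
| 1% | 7.6% (ncp 0.527) | 6.5% (0.395) | 5.9% (0.316) |
| 2% | 15.7% (1.054) | 10.9% (0.791) | 8.8% (0.632) |
| 3% | 29.3% (1.581) | 18.6% (1.186) | 13.6% (0.949) |

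With a gain of 1% the test is barely disturbed. With 3% and a small SD the rate is almost six times nominal.

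**The case against.** The strongest reply is that this is a declared open-label, single-arm pilot, that 6.3 is a template heading confined to randomization and blinding, and that some bias is unavoidable in such a design. Peak VO₂ is an instrument reading, effort measures are recorded at both tests, results are first described rather than tested, and averaging rules or effort checks may sit in a SAP or laboratory manual that is not shown.

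Much of this stands, and it limits what may be claimed. A reader might infer three stronger things:

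- **That the protocol abandons all control of bias.** It does not. The own-control comparison, the stable hydroxyurea dose, the transfusion exclusion, the exercise-lab quality control and the decision not to communicate expectations are all there.
- **That testers know the treatment status and the baseline value, and will push harder at the second test.** The protocol does not say what exercise-lab staff are told and does not mention encouragement. Their knowledge is a plausible inference from the open label and the fixed order, not a stated fact.
- **That the bias must favour voxelotor.** The hypothesis is directional, which makes that direction plausible, but nothing in the document establishes it.

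The reply does not rescue the reasoning in 6.3. That section takes a position, and the reason given for it does not address blinding or the conduct of the tests. That part of the bias cannot be removed is no ground for leaving the avoidable part without a rule. The recorded effort measures help only if someone is told to use them.

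**Conclusion.** The point holds in limited form. Section 6.3 draws a conclusion that its reason does not support, for an endpoint that depends on effort and whose second measurement is always on drug. A difference in effort between tests could be read as a voxelotor effect, and it would pass undiluted into the estimate of change.

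How large that difference would be, and in which direction, cannot be derived from the document. The rejection rates (6–8%, 9–16% and 14–29% for gains of 1%, 2% and 3%) rest wholly on the assumed gain, SD and significance level, and show sensitivity only. Because the results are first to be described, the shift in the estimate matters more than the rejection rate. The pilot remains feasible. The change is worth making because it is cheap and protects the study's main output.

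**What to change.** Replace the text of section 6.3 with:

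> Treatment is open-label. To limit assessment bias, (a) the same written encouragement script and the same treadmill protocol are used at both CPETs; (b) the baseline peak VO₂ is not displayed to staff or participant at the second CPET, and the baseline CPET report promised in 5.5 and 8.1 is released to the participant after the second CPET; (c) peak VO₂ is taken from both files by one fixed averaging rule with visit labels removed; (d) peak RER and peak HR, already recorded, are reported for both tests, with a sensitivity analysis limited to participants with RER above 1.1 at both.

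The parts do different work. Parts (a) and (b) act on effort during the test. Part (c) protects only the read-out and cannot undo an effort difference already recorded. Part (d) makes such a difference visible. Without the delayed release in (b), withholding the baseline value would be empty, since the participant might already hold the report. Sections 5.5 and 8.1 should state the same timing.

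**Cost.** Protocol wording, a short script and a uniform export of 20 files (10 participants × 2 tests) by existing staff, with no added visit or procedure. The participant's baseline report is delayed: on the nominal schedule in 1.3 (Day −29 to −1, then Day 60 to 89) by roughly 61 to 118 days, or about 9 to 17 weeks. Any safety-relevant finding is still communicated at once.

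**What remains.** Staff who ran both tests may remember the first value. Participant expectation, learning and time effects are not removed and should be stated as limitations.

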6.4 STUDY INTERVENTION COMPLIANCE

Each bottle of voxelotor contains 90 tablets. The dose is 3 tablets a day. Each bottle lasts 30 days. Participants will be scheduled for clinic visits no longer than 30 days apart. Participants will be given a bottle of voxelotor at a clinic visit and will be asked to bring back the bottle with left over pills in it. Compliance will be determined by pill counting. The number of pills remaining will be counted and subtracted from 90 to get the number of pills taken, which can be divided by 3 to get the number of days the drug was taken. The difference between the number of days drug was taken and the number of days between the clinic visits is the number of days drug was missed.

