1.2 SCHEMA

1.3 SCHEDULE OF ACTIVITIES (SOA)

| Procedures | Screening/ Enrollment Day -60 | Study Visit 1 Day -30 +/- 7 days | Study Visit 2 Day - 29 to -1 | Study Visit 3 Day 1 +/- 14 days | Study Visit 4 Day 30 +/- 7 days | Study Visit 5 Day 60 +/- 7 days | Study Visit 6 Day 60-89 | Final Study Visit 7 Day 90 +/- 14 days |
|--|-------------------------------------|--|------------------------------------|---------------------------------------|---------------------------------------|---------------------------------------|----------------------------|---|
| Informed consent | x | | | | | | | |
| Demographics | x | | | | | | | |
| Medical history | x | | | | | | | |
| Dispense voxelotor ^d | | | | x | x | x ^d | | |
| Concomitant Medication review | x | x | | x | x | x | | x |
| Physical exam | x | x | | x | x | x | | x |
| Vital signs, Ht, Wt | x | x | x | x | x | x | x | x |
| Performance status | x | | | | | x | | x |
| Routine labs ^a | x | x | | x | x | x | | x |
| Study labs ^b | | x | | | | x | | |
| Pregnancy test ^c | x | | | x | x | x | | |
| Adverse event review and evaluation | x | | | x | x | x | | x |
| Schedule CPET | | x | | | | x | | |
| CPET | | | x | | | | x | |
| CGI, PGI assessments | | | | | | | | x |
| Data collection and entry | x | x | | x | x | x | | x |

^a Routine labs: CBC diff, retic, CMP, LDH, haptoglobin, Hemoglobin F or hemoglobin electrophoresis

^b Study labs: Send to UCSF [name] lab: % F cells, P50 oxygen dissociation, ektacytometry, point of sickling (POS), dense cells.

^c Pregnancy test: All menstruating female participants

^d Participants will be treated with voxelotor for at least 8 weeks before the 2nd CPET, which will be scheduled as close to the date following 8 weeks of treatment with voxelotor. Participants will continue voxelotor until the 2nd CPET is completed.

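### Visit windows allow 36 to 44 days on a 30-day bottle, against the 30-day limit in Section 6.4 and the requirement to stay on drug until the second CPET

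*Protocol*

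**What the plan says.** Supply is described in three places. Section 6.1.2: "Voxelotor will be dispensed from the sickle cell clinic in bottles with 90 tablets each for a 30-day supply". Section 6.2.1: "Study drug will be dispensed at Visit 3 in bottles of 90 tablets". Section 6.4: "Each bottle of voxelotor contains 90 tablets", "The dose is 3 tablets a day" and "Each bottle lasts 30 days". Section 6.4 has the participant receive a bottle at a clinic visit and bring it back with whatever remains, and it limits the spacing: "Participants will be scheduled for clinic visits no longer than 30 days apart".

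The Schedule of Activities (Section 1.3) marks dispensing at Visits 3, 4 and 5 only. Each visit has its own window, for example "Study Visit 4 Day 30 +/- 7 days". Visit 3 is Day 1 with a tolerance of 14 days, Visit 5 is Day 60 with a tolerance of 7 days, and the second CPET (Visit 6) falls between Day 60 and Day 89. Footnote d asks for at least 8 weeks of treatment before that CPET, wants it held close to the 8-week date, and adds: "Participants will continue voxelotor until the 2nd CPET is completed".

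Sections 6.2.1 and 6.4 have leftover tablets returned and counted. Neither says whether they go back to the participant.

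**The concern.** The supply arrangement works only if the next bottle arrives within 30 days, and the visit windows do not ensure that. A participant whose visits are all inside their windows can run out of tablets and wait for the next visit. Three bottles may cover the period in total, but the second and third are handed over only at Visits 4 and 5, so the total does not protect any single interval.

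Two things are at stake. First, the primary endpoint rests on one baseline and one on-drug peak VO₂ per participant (Section 9.4.2), in 10 participants (Section 9.2). Section 2.3.1 says drug-modified hemoglobin degrades once voxelotor stops, so a gap shortly before the second CPET would tend to weaken whatever effect the drug has. Second, the adherence measure in Section 6.4 cannot tell a day with no tablets from a day when tablets were not taken.

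**Working it through.** **Days per bottle.** 90 tablets / 3 per day = 30 days, which reproduces the figure in Section 6.4.

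**Nominal spacing.** Visit 3 to 4: 30 − 1 = 29 days. Visit 4 to 5: 60 − 30 = 30 days. Visit 5 to the last CPET day: 89 − 60 = 29 days. The nominal calendar fits the 30-day limit.

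**Longest spacing inside the windows.** This is the latest day of the later visit minus the earliest day of the earlier one. The windows are Visit 4 Days 23 to 37, Visit 5 Days 53 to 67, CPET Days 60 to 89. Visit 3 is taken first as Day 1, then at the early edge of its window (Day −13, counting through a Day 0). The CPET is taken to come after Visit 5, where it is scheduled.

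| Interval | Longest | Beyond one 30-day bottle |
|---|---|---|
| Visit 3 to 4, Visit 3 at Day 1 | 37 − 1 = 36 days | 6 days |
| Visit 3 to 4, Visit 3 at Day −13 | 37 − (−13) = 50 days | 20 days |
| Visit 4 to 5 | 67 − 23 = 44 days | 14 days |
| Visit 5 to second CPET | 89 − 53 = 36 days | 6 days |

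The right-hand column assumes that leftovers are not handed back. The 50-day row also needs later visits to be counted from a nominal Day 1 after an early first dispensing. The 44-day row does not depend on Visit 3.

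**If leftovers are kept and Visit 3 is Day 1.** Two bottles give 2 × 30 = 60 days, Days 1 to 60, provided Visit 4 comes before the first bottle runs out. The third bottle comes at Visit 5, which may be Day 67. Days 61 to 66 are then uncovered: 6 days. Drug resumes on Day 67, and a CPET on Day 68 is inside its window. The 8-week minimum does not screen this schedule out, because 60 days on drug already exceed 8 × 7 = 56.

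**Gap running right up to the CPET.** At most 6 days (Visit 5 on Day 53, CPET on Day 89). It needs leftovers not returned, or Visit 3 before Day 1. With leftovers kept and Visit 3 at Day 1 it is 0 days.

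**Pill count.** Section 6.4 takes days on drug as (90 − tablets remaining) / 3, and days missed as the days between visits minus that. A fully adherent participant with a 44-day interval returns an empty bottle: (90 − 0) / 3 = 30 days taken, and 44 − 30 = 14 days missed. All 14 are days with no supply. Subtracting from 90 each time also presumes that every interval starts with exactly 90 tablets, which sits poorly with keeping leftovers.

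**The case against.** The strongest reply is that both rules can be met together. Section 6.4 governs how visits are booked, the windows are tolerances around nominal days, and the nominal days are 29 and 30 days apart. On that reading a 44-day interval already breaches Section 6.4. It stands that careful booking avoids every gap shown here, and that these are extreme schedules rather than expected ones. But the protocol nowhere says that the 30-day limit narrows the windows, and windows exist for visits that slip.

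A second reply is that footnote d wants the CPET close to 8 weeks, so a Day 89 test is unlikely. That is fair for the 6-day gap after Visit 5. It does not help with Days 61 to 66, since the same instruction draws the CPET closer to a late Visit 5.

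Stronger readings are tempting and are not supported:

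- A reader might infer that three bottles are too few in total. With Visit 3 at Day 1 the longest route to the CPET is 89 − 1 = 88 days, within 3 × 30 = 90. A shortfall in total needs an early Visit 3.
- A reader might infer that Section 7.1 is breached, because it requires a month of continuous drug before the CPET. That rule is written for a participant who discontinues and resumes. Whether a supply gap counts is not stated.
- A reader might infer that a supply gap leads to withdrawal. Section 7.2 leaves withdrawal for significant non-compliance to the investigator, and the formula yields a count of days without assigning blame.

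**Conclusion.** The conflict holds. One 30-day bottle per visit and a 30-day limit on spacing do not fit windows that allow 36 days (Visit 3 at Day 1) or 44 days between dispensing visits, and 36 days from the last dispensing to the second CPET. Without return of leftovers, up to 6, 14 and 6 days are uncovered. The first figure becomes 20 only if Visit 3 may fall on Day −13 with later visits still counted from Day 1. On the more favourable assumptions (leftovers kept, Visit 3 at Day 1), up to 6 days just before Visit 5 remain uncovered, and the CPET can come soon afterwards. A schedule that respects every window can therefore fail footnote d ahead of the only on-drug measurement of the primary endpoint.

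The effect on the endpoint cannot be sized. The protocol gives no time course for loss of effect, and dilution presupposes that there is an effect to dilute. It would be wrong to conclude that participants will generally be off drug at the CPET. The documents show only that the plan permits an interruption and, as written, would record it as missed doses.

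**What to change.** Reconcile the visit windows and footnote d in Section 1.3 with the 30-day spacing and supply statements in Sections 6.1.2, 6.2.1 and 6.4, and say which governs when a visit slips. That choice is the sponsor's. State whether leftover tablets are returned to the participant, and make the pill-count formula agree with the answer. Record the date of the last dose at the second CPET. Report days without dispensed supply separately from missed doses.

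The cost is wording in these sections and one extra data field.
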